5.10 Patient-Reported Outcomes Measurement Information System (PROMIS®)

To study the side effect profile of patients treated with transdermal buprenorphine and tramadol, we will use (PROMIS®) questionnaires. We will use PROMIS® cognition and gastrointestinal side effect assessment questionnaires for our secondary outcome analysis. For example, PROMIS® GI Symptom instrument has 60 items and assesses eight domains: gastroesophageal reflux (13

items), disrupted swallowing (seven items), diarrhea (five items), bowel incontinence/soilage (four items), nausea and vomiting (four items), constipation (nine items), belly pain (six items), and gas /bloating /flatulence (12 items). For the study purposes, we will only be using disrupted swallowing, constipation and nausea/vomiting forms. A higher score denotes more GI symptoms. Similarly, the PROMIS® Applied Cognition short form has four questions. A higher cognition score would denote more cognitive impairment. The recall period for PROMIS® GI Symptom items is around one week. We will be collecting PROMIS® data weekly through an in-person visit or through telephone interviews for up to 12 weeks. We hope to quantify and measure severity of study regimen-related side effects. We also plan to record frequency of antinausea, laxative and oral anesthetic use. We expect that buprenorphine will have manageable GI and cognitive side effect profile. (25, 26) The PROMIS® GI and cognition forms are included in appendix section of this protocol.

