1 BACKGROUND

1.1 Head and Neck Squamous Cell Carcinoma

Head and neck squamous cell carcinoma (HNSCC) is the eighth most common cancer in the United States with more than 53,600 new cases diagnosed annually.(1) Early-stage or locally advanced head and neck cancer patients are typically treated by a multimodality approach including surgery, radiation and chemotherapy. Mucositis-related pain and dysphagia are two of the most common primary toxicities associated with head and neck radiation. Around 80–100% of head and neck cancer patients being treated with radiation therapy suffer from oral mucositis pain. Severe mucositis (WHO grades 3 and 4) occurs in 25% of patients when standard fractionated radiation (once-daily dose) is used as a single modality. The incidence of severe mucositis can be as high as 50%–75% when radiation is used in conjunction with concurrent radio-sensitizing chemotherapy. (2, 3)

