8 STATISTICAL CONSIDERATIONS

8.1 Study Endpoints

8.1.1 Primary endpoint: Establish efficacy of study regimen by showing that at least 33% of patients will achieve at least a 30 percent decrease in VAS pain score from baseline to the end of week 9 of treatment and follow-up period. Earlier studies have shown that the VAS pain score ($\geq 4/10$) on the day of treatment initiation can be used as baseline in this setting and a 30% or higher reduction in baseline pain score is a sign of meaningful drug response.(27-29)

8.1.2 Secondary endpoint:

1. Monitor compliance of study drug regimen through OM Pain App and medication diary.

2. Identify study participants who require off-protocol opioids for pain control despite being on the highest dose of study drug combination.
3. Correlate cumulative mean weekly pain scores calculated by the pain app with the average weekly pain scores recorded by the BPI short form.
4. Correlate average weekly OM Pain App scores and average weekly pain scores calculated from the BPI short form with head and neck symptoms and function evaluation tool MDASI-HN. The cumulative average area under the curve (AUC) weekly pain scores are expected to be inversely proportion to MDASI-HN average weekly AUC physical activity scores.
5. Maintain a weekly log of use of other nonopioid supportive care medications, such as laxatives, antiemetics, and oral anesthetics, in conjunction with the study drug combination during treatment and follow-up period through weekly questionnaires. Average weekly use of laxatives and antiemetics is expected to decrease by the end of follow up period.
6. Assess incidence and severity of gastrointestinal and cognitive side effects of the study drug regimen and their impact on quality of life, as measured by weekly PROMIS® (GI and cognition) questionnaires.
7. Safety: Assess the incidence and severity of other adverse events associated with the study drug combination using CTCAE version 5.

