2. Rarely
3. Sometimes
4. Often

5. Always

GISX 3)

How often did you have a poor appetite?

1. Never
2. Rarely
3. Sometimes
4. Often
5. Always

In the past 7 days...

GISX4)

How often did you throw up or vomit?

1. Never
2. One day
3. 2-6 times per day
4. Once a day
5. More than once a day

PROMIS® questionnaires can be downloaded directly from

<https://www.healthmeasures.net/explore-measurement-systems/promis/obtain-administer-measures>

BRIEF PAIN INVENTORY (SHORT FORM)

Patient Initials:

Date of Birth (dd, mm, yyyy):

[figure not shown]
Visit Date (dd, mm, yyyy):

1. Throughout our lives, most of us have had pain from time to time (such as minor headaches, sprains, and toothaches). Have you had pain other than these everyday kinds of pain during the last week?

Yes

No

[figure not shown]
2. On the diagram, shade in the areas where you feel pain. Put an X on the area that hurts the most.

3. Please rate your pain by circling the one number that best describes your pain at its **worst** in the last 24hours.

4. Please rate your pain by circling the one number that best describes your pain at its **least** in the last week.

5. Please rate your pain by circling the one number that best describes your pain **on the average weekly**.

[figure not shown]

6. Please rate your pain by circling the one number that tells how much pain you have **right now**.

7. What treatments or medications are you receiving for your pain?

8. In the last week, how much relief have pain treatments or medications provided? Please circle the one percentage that most shows how much **relief** you have received.

9. Circle the one number that describes how much, during the past week, pain has interfered with your: A. General Activity

B. Mood

[figure not shown]
C. Walking Ability

D. Normal Work (includes both work outside the home and housework)

E. Relations with other people

F. Sleep

G. Enjoyment of life

Scoring:

Pain Severity Score = Mean of items 3-6 (pain at its worst, pain at its least, average Pain
 Interference Score = Mean of items 9A-9G (interference of pain with: general activity, mood, walking, normal work, relations, sleep, enjoyment of life)

MDASI- HN questionnaires

Forms can be obtained from MDASI website

<https://www.mdanderson.org/research/departments-labs-institutes/departments-divisions/symptom-research/symptom-assessment-tools/md-anderson-symptom-inventory-head-and-neck-cancer-module.html>

REFERENCES

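### The PROMIS Disrupted Swallowing form is counted as a regimen side effect although the protocol treats dysphagia as a radiation toxicity, and one printed answer option on the vomiting item is out of order

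*Combined protocol and SAP*

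**What the plan says.** Secondary endpoint 6 (Sections 2.5 and 8.1.2) is to assess the incidence and severity of "gastrointestinal and cognitive side effects of the study drug regimen and their impact on quality of life", measured weekly by PROMIS. Section 5.10 chooses the GI content: "we will only be using disrupted swallowing, constipation and nausea/vomiting forms". It gives the purpose as follows: "We hope to quantify and measure severity of study regimen-related side effects". It also says that the forms are in the appendix.

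Other sections bear on how these scores can be read:

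- Section 1.1: "Mucositis-related pain and dysphagia are two of the most common primary toxicities associated with head and neck radiation".
- Section 5.1 starts the regimen only when radiation mucositis of at least grade 1 is seen together with pain. It also recognises that chemotherapy and radiation can confound adverse event assessment.
- Section 6.1.1 counts GI effects as adverse events for this study only where they are not attributable to radiation or chemotherapy. No equivalent rule is given for PROMIS.
- Section 8.6 summarises PROMIS by mean, standard deviation, median and range. It adds patient-level AUC of weekly averages, scatterplots, Spearman correlation and regression.

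In Appendix 4, the third of the five answers to the vomiting item is "2-6 times per day". It stands between one day and once a day. The first constipation item uses the same ladder but prints two to six days in that slot.

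**The concern.** A swallowing score collected in patients who all have radiation mucositis should largely follow the mucositis. If the regimen relieves pain, the score may even improve while it is being reported as toxicity. A reader of the results would then take a radiation effect for part of the drug's side-effect profile. The background (Sections 1.3 and 1.5.5) presents milder side effects as part of the case for buprenorphine, so the labelling matters.

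The vomiting item is a separate and smaller matter. With the printed options, a patient who vomits more often can receive a lower score than one who vomits less often.

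**Working it through.** **Item counts.** Section 5.10 says that the "PROMIS® GI Symptom instrument has 60 items and assesses eight domains". The listed domain counts give 13 + 7 + 5 + 4 + 4 + 9 + 6 + 12 = 60 over eight domains, so the stated figure reproduces. The three chosen forms hold 7 (swallowing) + 9 (constipation) + 4 (nausea/vomiting) = 20 items, and Appendix 4 prints the same numbers.

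- Swallowing share: 7/20 = 35%.
- Items left for the regimen GI profile without swallowing: 20 − 7 = 13.
- Items with neither defect: 20 − 7 − 1 = 12, or 60%.

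**What the swallowing form asks, against the protocol's own account.**

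- The seven items cover food sticking in the chest or throat, chest pain on swallowing, and difficulty with solids, soft foods, liquids and pills. None asks about cause.
- The WHO mucositis scale (Appendix 3) grades II to IV by whether solids, only liquids, or no oral intake is possible. The two instruments therefore overlap.
- Section 5.11 lists difficulty swallowing or chewing in MDASI-HN as a symptom relevant to head and neck cancer. The same complaint is a cancer symptom on one form and a drug side effect on another.
- The common drug effects in Sections 7.1.5 and 7.2.5 include nausea, vomiting and constipation. Dysphagia is not listed.

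**The vomiting item as printed.** In order, the options are: 1 never, 2 one day, 3 "2-6 times per day", 4 once a day, 5 more than once a day.

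- Option 3 implies 2 × 7 = 14 to 6 × 7 = 42 episodes a week; option 4 implies 7. The order is reversed.
- A patient vomiting three times a day can truthfully tick 3 or 5, a difference of 5 − 3 = 2 points. By ticking 3, that patient scores below someone vomiting once a day, who ticks 4.
- A patient vomiting on three days of the week has no matching option.
- The protocol states no scoring method. If raw item scores are summed (an assumption), the nausea/vomiting range is 4 to 20, a width of 16, and the ambiguity is 2/16 = 12.5% of it.

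**The case against.** The strongest reply is that little is actually damaged. A reader might infer that GI toxicity of the regimen as a whole is mis-measured, or that 35% is the size of a bias. The documents support neither. No section pools the three forms, so swallowing cannot contaminate the constipation or nausea/vomiting results. Constipation and three of the four nausea/vomiting items have neither defect.

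The planned AUC and correlation analyses could show whether swallowing tracks mucositis pain, so it would also be wrong to say that only average levels are reported. The confounding is partly acknowledged: Section 5.1 looks to the period after radiation for clearer side-effect assessment, and Section 6.1.1 restricts GI adverse events. Two of the seven swallowing items concern the chest. Dry mouth is listed for both drugs, so some drug contribution to swallowing difficulty cannot be excluded.

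On the vomiting item, Appendix 4 says that PROMIS forms can be downloaded from the source site. The misprint may therefore never reach a patient. Options 1, 2, 4 and 5 remain in order, so it would go too far to say that the item cannot rank patients at all.

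All of that stands, and it limits the point. It does not remove it. None of these provisions supplies an attribution step for PROMIS. The post-radiation period does not resolve the matter either, because Section 5.1 expects most patients to have moderate to severe mucositis pain until week 12. Section 5.10 points to the appended forms, so the version in use needs to be confirmed.

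**Conclusion.** The point holds in limited form. The plan places a form that mainly reflects radiation toxicity under side effects of the study regimen, with no rule for separating the two. One of the 20 printed GI items also has a misordered, overlapping answer option, and its effect depends on which version patients complete. The wording of the parallel constipation item suggests a transcription slip but does not prove one.

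The reach is one secondary, descriptive endpoint. Sample size, the decision rule and the primary test are untouched. The 35% describes how much of the selected GI content is affected by the labelling; no bias can be calculated from the documents. The 2-point ambiguity (12.5% of the nausea/vomiting range) rests on the assumption of raw scoring. The change is worth making because it is cheap and prevents a wrong label in the results.

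**What to change.** 1. In Sections 2.5, 5.10 and 8.1.2 (and the matching summary entry), take Disrupted Swallowing out of endpoint 6. Report it as a mucositis and function outcome alongside MDASI-HN.
2. State that constipation and nausea/vomiting are reported as separate forms. Add change from the treatment-start form to the planned summaries, with that form completed before the first dose. Its recall of about one week then covers the period before the drug.
3. State that change from treatment start does not isolate a drug effect while radiation or chemotherapy continues.
4. Check option 3 of the vomiting item against the source PROMIS form and correct it, apparently to 2-6 days. Record which version was administered, and flag any answers collected on the misprinted form.

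Cost: wording in a few sections and one answer option, with no added visits or items. The downsides are that the treatment-start form must be completed before dosing, and that the regimen GI profile rests on 13 items instead of 20.

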APPENDIX 4. QUESTIONNAIRES

PROMIS® – COGNITIVE FUNCTION- SHORT FORM

Please respond to each question or statement by marking one box per row in the past seven days.

		Never	Rarely (Once)	Sometimes (Two or three times)	Often (once a day)	Very often (Several times)
PC2r	My thinking has been slow	 5	 4	 3	 2	 1
PC35r	It has seemed like my brain was not working as well as usual	 5	 4	 3	 2	 1
PC36r	I have had to work harder than usual to keep track of what I was doing	 5	 4	 3	 2	 1
PC42r						

	I have had trouble shifting back and forth between different activities that require thinking	5	4	3	2	1
--	--	---	---	---	---	---

PROMIS® Gastrointestinal Disrupted Swallowing

Please respond to each question or statement by marking one box. In the past seven days...

		Never	Rarely	Sometimes	Often	Always
GISX31	How often did food get stuck in your chest when you were eating?	 1	 2	 3	 4	 5
GISX32	How often did food get stuck in your throat when you were eating?	 1	 2	 3	 4	 5
GISX33	How often did you feel pain in your chest when swallowing food?	 1	 2	 3	 4	 5
GISX34	How often did you have difficulty swallowing solid foods like meat, chicken or raw vegetables, even after lots of chewing?	 1	 2	 3	 4	 5
GISX35	How often did you have difficulty swallowing soft foods like ice cream, apple sauce, or mashed potatoes?	 1	 2	 3	 4	 5

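### Section 5.10 reads the PROMIS cognition score in the opposite direction to the codes on the appended form, with no recoding stated, so cognitive worsening can be reported as improvement

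*Combined protocol and SAP*

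**What the plan says.** Section 5.10 gives the reading rule for the gastrointestinal forms first: "A higher score denotes more GI symptoms". It then carries the same direction over to cognition: "A higher cognition score would denote more cognitive impairment". It describes the instrument by saying that the "Applied Cognition short form has four questions", and it tells the reader that the "GI and cognition forms are included in appendix section of this protocol".

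In Appendix 4 the cognition page is headed "COGNITIVE FUNCTION- SHORT FORM". It has four items, all describing a difficulty, for example "It has seemed like my brain was not working as well as usual". Each is coded Never = 5, Rarely = 4, Sometimes = 3, Often = 2, Very often = 1. The seven-item swallowing form that follows, with items such as "How often did you have difficulty swallowing soft foods like ice cream, apple sauce, or mashed potatoes", is coded the other way, from Never = 1 to Always = 5.

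Section 8.6 plans the mean, standard deviation, median and range for the PROMIS measures, patient-level AUCs of weekly averages for the patient-reported outcomes, and Spearman correlations. It gives no scoring direction. The only scoring note in Appendix 4 belongs to the Brief Pain Inventory.

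**The concern.** One reading rule, higher is worse, is applied to two forms whose printed codes run in opposite directions. It fits the swallowing form and contradicts the cognition form. An analyst who scores the cognition form as printed and interprets it from 5.10 would report decline as benefit.

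This matters because the Protocol Summary makes PROMIS the measure of cognitive adverse events in secondary endpoint 6, and Section 1.5.5 says that the cognitive effects of the patch have not been studied extensively in these patients. The trial has a single arm (Section 8.2), so no control group would expose a reversed score.

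**Working it through.** The plan gives no numerical figure to reproduce here; the check is one of direction.

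**Inputs.** Four cognition items coded 5 to 1 and seven swallowing items coded 1 to 5 (Appendix 4); higher is worse for both (Section 5.10). Assumption: the score is the sum or mean of the printed codes, because the plan states no method.

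**Step 1, cognition as printed.** Sum = 4 × code.
- All Never: 4 × 5 = 20
- All Often: 4 × 2 = 8
- All Very often: 4 × 1 = 4

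Going from Never to Often on all items changes the sum by 8 − 20 = −12, or the item mean from 5.0 to 2.0. Under 5.10 a fall means less impairment, so this worsening reads as improvement. The patient without problems has 20 of 20, which 5.10 would call the most impaired score.

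**Step 2, swallowing as printed.** Sum = 7 × code.
- All Never: 7 × 1 = 7
- All Often: 7 × 4 = 28

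The same shift in answers changes the sum by +21, or the mean from 1.0 to 4.0, which 5.10 correctly reads as worse. Identical worsening therefore looks like harm on one form and benefit on the other.

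**Step 3, cognition recoded as 6 minus item.** The sum over four items is 4 × 6 − printed sum = 24 − printed sum. All Never becomes 24 − 20 = 4, all Often 24 − 8 = 16, all Very often 24 − 4 = 20. The example now moves from 4 to 16, in the direction that 5.10 states.

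**Step 4, correlations.** If the patient-level summary is divided by the weeks observed, the recoded value is 24 − printed value. All ranks reverse, and Spearman's coefficient keeps its size and changes sign exactly.

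Section 8.6 does not mention that division. Without it, recoded AUC = 24 × weeks − printed AUC, and the number of weeks can differ because PROMIS collection begins only when study treatment begins (Section 3.2). Two invented patients show the consequence, taking AUC as weeks × constant score:
- A, 4 weeks at a printed score of 16: printed AUC 4 × 16 = 64; recoded 24 × 4 − 64 = 32
- B, 8 weeks at a printed score of 10: printed AUC 8 × 10 = 80; recoded 24 × 8 − 80 = 112

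B ranks above A both ways. With an undivided AUC the coefficient may change in size or in sign, but a clean reversal does not follow.

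**The case against.** **The form may be a different one.** Section 5.10 speaks of Applied Cognition, the appendix of Cognitive Function, and Appendix 4 adds that the "questionnaires can be downloaded directly from" the source site. If another form is used, 5.10 could be right for it and the appendix page wrong. This stands as a reason to check first. It does not remove the conflict, because 5.10 itself points to the appendix and both descriptions have four items.

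**A published scoring rule may be applied.** Section 5.10 cites instrument papers, which cannot be consulted here. But any score that rises with the printed codes keeps their direction, so only a reversal would make 5.10 true, and the plan states none.

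**Stronger readings.** A reader might infer that every correlation using the score has the wrong sign. Step 4 shows that this is certain only for a per-week average. Moreover, the correlations named as endpoints (8.1.2, items 3 and 4) involve the pain app, the BPI and MDASI-HN; cognition enters only through the general wording of 8.6. A reader might also infer that symptom management would be misdirected, since Section 1.5.5 links PROMIS data to timely interventions. The documents give no PROMIS threshold that triggers action, and staff see answers labelled in words on the form.

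**Conclusion.** The contradiction between Section 5.10 and the appended form is certain and needs no outside source. The misreport is conditional: it occurs if the printed codes are scored without reversal and then read by the 5.10 rule. On a sum, the example is 20 to 8, a change of −12 reported as improvement when it is a decline. The direction does not depend on choosing sum or mean, only on the score rising with the printed codes. The documents do not show that a misreport will happen, because no scoring method is given either way.

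The reach is narrow. It covers the cognition component of one of seven secondary endpoints, which is analysed descriptively. CTCAE events, including central nervous system depression (Section 6.1.1), are recorded separately. The primary binomial test and the GI scores are unaffected. The point should be corrected before analysis, but it does not threaten the trial's main conclusion.

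**What to change.** First confirm which cognition form patients complete, and use one instrument name in Section 5.10 and Appendix 4.

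If it is the appended form, state one of these in 5.10 and 8.6 before analysis:
- cognition is scored as printed, and higher means better function; or
- each cognition item is recoded as 6 minus item before scoring, and higher means more impairment.

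If it is a different form, replace the appendix page and state that form's direction in both sections.

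In each case say how the items are combined into a score. The cost is about one sentence in each section, one form check, and one line of scoring code if items are recoded. No new data, visits or patients are needed.

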5.11 Other Functional, Symptom Assessments

A compliance questionnaire that has been previously used to test an electronic pain diary will be administered periodically by the study coordinator, as per study calendar. The coordinator who is trained in using the WHO mucositis scale will grade mucositis weekly during radiation therapy. The Brief Pain Inventory questionnaire and MDASI-HN will also be administered weekly during radiation therapy and the follow-up period, as per study calendar. These questionnaires can also be administered through a telephone interview by a provider or CRC. All responses in the BPI (24) short form will be recorded, including severity of pain, impact of pain on daily function, location of pain, pain medications, and amount of pain relief in the past 24 hours or the past week

MDASI consists of 28 question items. Along with the core MDASI's 13 symptom items and six interference items, the MDASI-HN (21) also assesses nine symptoms relevant to head and neck cancer, such as mucus in the mouth and throat, difficulty swallowing or chewing, choking or coughing, difficulty with voice or speech, skin pain/burning/rash, constipation, problems with tasting food, mouth/throat sores and problems with teeth or gums. Copies of the BPI and MDASI forms are included in appendix section of this protocol.

